The TC comparator arm options and doses are described in greater detail in Section 7.2 and treatment duration will be based on approved prescribing information and institutional standard practice. Guadecitabine will be given SC at a dose of 60 mg/m² in 28-day cycles. For the first cycle guadecitabine will be given for 10 days on Days 1-5 and Days 8-12 or on Days 1-10. The second cycle will be either the 5-day regimen (Days 1-5) or 10-day regimen (Days 1-5 and 8-12 or Days 1-10) based on assessment of disease response and hematological recovery at the end of Cycle 1. In subsequent cycles guadecitabine treatment will be for 5 days only (Days 1-5). Guadecitabine treatment should be given for at least 6 total cycles in the absence of unacceptable toxicity or disease progression requiring alternative therapy. Beyond 6 cycles, treatment should continue as long as the subject continues to benefit based on investigator judgment.

Treatment cycles are intended to be repeated every 28 days. However, treatment delays are permitted to allow normal count hematological recovery in the absence of PB blasts, particularly with more intensive treatment such as guadecitabine 10-day regimen, HiDAC, MEC, and FLAG/Ida. Visits will occur on treatment days, as necessary. In addition, during the first 3 cycles, visits will occur weekly on Days 8, 15, and 22, then on Day 15 in Cycles 4-6. In Cycles >6, visits will only occur on treatment days (if necessary), with study specified assessments on Day 1. Additional visits based on treatment effect and blood counts may be done at the investigator's discretion. Subjects will attend a safety follow-up visit after the last study treatment. For subjects who discontinue study treatment before Cycle 6, long term follow-up visits will occur monthly until 6 months after the start of study treatment and then every 3 months thereafter. For subjects who discontinue study treatment after Cycle 6, long-term follow-up will be every 3 months.

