7.3 Guidelines for Adjusting or Withholding Study Treatment

7.3.1 Guidelines for Guadecitabine

Guadecitabine study therapy is intended to be administered for a minimum of 6 total cycles.

Dosing for the first 2 cycles is described in Section 7.1.2. Timing of cycle initiation and dose level of guadecitabine starting at Cycle 3 will be guided by PB blast and neutrophil/platelet counts after the prior cycle, as indicated in Table 5, which describes dose modification based on Day 29 or later PB counts.

Table 5:Guadecitabine Dosing Adjustment Guideline Based on Peripheral
Blood Blasts and Counts (for Cycles ≥3)

Neutrophils	Peripheral	No Peripheral Blood Blasts								
Platelets	Blood Blasts Present	On Day 1 of Next Intended Cycle	Recovery After ≤1-Week Dose Delay	Recovery After >1-Week Dose Delay						
ANC ≥500/µL AND Platelets ≥50,000/µL	Full dose (5-day	Full dose (5-day regimen) on schedule	Full dose (5-day regimen) after recovery	Reduce 1 dose level after recovery (5-day regimen)						
ANC <500/µL OR Platelets <50,000/µL	regimen) on schedule	Consider dose delay or reduction								

For subjects with CRh, CRi or CRp for at least 2 cycles, guadecitabine treatment may be reduced 1 dose level at a time in each subsequent cycle to allow for normal counts recovery to levels of full CR (neutrophils $\geq 1000/\mu$ L and platelets $\geq 100,000/\mu$ L). The highest dose level that achieves normal counts recovery should be kept for subsequent cycles. Recommended reduced guadecitabine dose levels should be from 60 mg/m²/day to 45 mg/m²/day, then to 30 mg/m²/day, and then to 15 mg/m²/day with the Daily×5 regimen.

Subjects with highly proliferative disease between cycles could receive subsequent cycles earlier than the intended 28-day cycle interval (such subsequent cycles could begin any time after treatment is completed in the preceding cycle).

Beyond 6 cycles, treatment should continue at the dose level reached as long as the subject continues to benefit based on investigator judgment and subject response and tolerability.

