Quality of Life: Health-related QOL will be assessed using the EQ-5DTM, which is a standardized instrument for use as a measure of health outcome. QOL assessments will consist of the EQ-5D level health questionnaire (EQ-5D-5L) and the EQ VAS which will be administered before treatment on Day 1 of each cycle for 6 cycles and then at every study visit until disease progression; for subjects who discontinue study treatment before Cycle 6, QOL will be assessed monthly until 6 months after the start of study treatment, then at every study visit until disease progression.

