Laboratory Assessments	Screening ^f (D -14 to -1)					•	•	•						•		•	•		
Hematology ^m	X	X ^m				Х			Х	Х	X ^m						Х	X	Xc
Serum chemistry ⁿ	X	X ⁿ									X ⁿ							Х	
Urinalysis	X																		
Serum or urine pregnancy test ^o	X	Х									Х							Х	
Disease Assessments			1	-	1	1		1	1	1				-	1	1	1		
BM aspirate or biopsy ^r	X	Xr									Xr								Xc
Cytogenetics	X																		
Hospitalizations/Transfusions ^s	X	Х									Х							X	Xc
Subsequent anti-leukemic therapy																		х	Х
Disease progression status ^t																		X	Xc
Survival follow-up																		Х	Х

^a The Day 15 visit is not required after Cycle 6.

Safety follow-up visit: Must occur 30 (+7) calendar days after the last dose of study treatment or before the subject starts another anti-leukemia therapy for AML (except for hydroxyurea as specified in Section 7.4.1), whichever occurs first. If the subject cannot attend the clinic, the visit may be conducted by telephone to collect, at minimum, AE, hospitalizations/transfusions, subsequent anti-leukemic therapy, QOL responses and survival information. Safety follow-up visit may occur at the same time as treatment discontinuation only if decision to permanently discontinue treatment is made at least 30 days after last dose.

^c Long-term follow-up visits: Start after treatment discontinuation. Monthly (±7 days) visits are required for subjects who discontinue study treatment before Cycle 6, until 6 months after the start of study treatment. After monthly visits for at least 6 months, long-term follow-up visits will be every 3 months (±2 weeks) until death. The first long-term follow-up visit should occur 1 month or 3 months (whichever applies) after the safety follow-up visit or after the last dose of study treatment, whichever applies. Monthly and quarterly visits may be conducted by telephone if needed. Refer to Section 9.5.6 for the specific assessments to be performed at the long-term follow-up visits.

Astex Pharmaceuticals, Inc. Clinical Protocol SGI-110-06

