- ⁱ **12-Lead ECG (triplicate):** Conduct predose and 1-2 hours postdose only on Day 1 of Cycle 1, and at safety follow-up visit. Subjects in BSC arm: Conduct ECG (in triplicate) on Cycle 1 Day 1, and at the safety follow-up visit. Acquire and review according to institutional procedure (rhythm, atrial rate, ventricular rate, PR interval, QRS duration, and QT/QTc, morphology and overall interpretation). The QT correction method should be the same for all ECGs for a given subject. Clinically significant abnormal ECG at study treatment discontinuation as compared to the predose ECG should be followed for recovery or stabilization.
- ^j Health-related QOL: Administer EQ-5D-5L and EQ VAS before treatment on Day 1 of each cycle for 6 cycles, then at every study visit until disease progression. For subjects who discontinue treatment before Cycle 6, administer EQ-5D-5L and EQ VAS monthly until 6 months after the start of study treatment, then at every study visit until disease progression.
- k Weight and BSA calculation: Weigh subjects on Day 1 of each cycle. BSA recalculation is only required if weight changes ±10% or more from the last calculation.
- ¹ Concomitant medications: Document all medications taken within 14 days before randomization to 30 days after the last dose of study treatment, or start of new anti-leukemic treatment for AML (except for hydroxyurea as specified in Section 7.4.1), whichever is first.
- ^m Hematology: Include complete blood count with WBC differential (a manual count should be conducted if there is suspicion of PB blasts). Day 1 hematology for all cycles does not need to be repeated if done within 4 days of Day 1. Additional hematology assessment may be done for safety or for subject management at the investigator's discretion. Collection, analysis, and reporting information are described in the Study Laboratory Manual.
- ⁿ Serum chemistry: Refer to Table 8. Day 1 chemistry for all cycles does not need to be repeated if done within 4 days of Day 1. Additional chemistry assessment may be done for safety or for subject management at the investigator's discretion. Collection, analysis, and reporting information are described in the Study Laboratory Manual.
- Pregnancy test: Women of child-bearing potential only. The screening test must be done within 7 days of Cycle 1 Day 1 (ie, Day -7 to -1); test not required on Cycle 1 Day 1 if done at screening.

r

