7.3.2.10 EQ-5D-5L Descriptive System Total Score and the EQ VAS

The EQ-5D-5L descriptive system scores and the EQ VAS were collected for each subject for a minimum 6 months unless the subject died or withdrew consent prior. The calculation for EQ-5D-5L index value will be performed according to EuroQol group's EQ-5D-5L User Guide (http://www.euroqol.org/about-eq-5d.html). Since there are only a limited number of countries which have rules available for calculating EQ-5D-5L index values, the rules for England (Devlin et al 2016) will be used for all subjects from all countries in this study. These analyses will include only the data collected for each subject during the first 6 months of study participation.

As suggested in the EQ-5D-5L User Guide (http://www.euroqol.org/about-eq-5d.html), the EQ-5D-5L descriptive scores and their dichotomized levels (No problems, Problems) within each EQ-5D dimension (mobility, self-care, usual activity, pain/discomfort, anxiety/depression), will be summarized by time (ie, visit/treatment cycle) descriptively, using counts and proportions. The EQ-5D-5L index value and VAS and their respective changes from baseline will be summarized by time (ie, visit/treatment cycle) using means, standard deviations, medians, and quartiles.

In addition, the changes from baseline (post baseline value – baseline value) of EQ-5D-5L index value, and separately EQ VAS, will be analyzed using a mixed model approach for repeated measures. This model will include the following terms as fixed effects: baseline value, treatment, time, and treatment-by-time interaction. The unstructured covariance matrix will be used to account for the within subject correlation and allow for different variances at different measurement times. The difference of the least squares means between the two treatment groups at each time (ie, visit/treatment cycle) and its corresponding 95% CI will be provided.

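### The SAP analyses EQ-5D by visit or treatment cycle, so equal time labels can mean different days since randomization, and off-treatment records have no cycle label

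*SAP*

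**What the plan says.** **Collection.** Footnote j to Table 7 (Protocol 9.5.1) ties on-treatment assessment to the cycle: "Administer EQ-5D-5L and EQ VAS before treatment on Day 1 of each cycle for 6 cycles". For subjects who stop before Cycle 6 it switches to the calendar: "administer EQ-5D-5L and EQ VAS monthly until 6 months after the start of study treatment". Protocol 9.1 agrees. EQ-5D is also taken at the safety follow-up visit, which "Must occur 30 (+7) calendar days after the last dose of study treatment", or before another anti-leukemia therapy starts if that is earlier. Protocol 9.5.6 counts the first long-term follow-up visit from the safety visit or the last dose, not from randomization.

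**Cycle timing.** Cycles are nominally 28 days, but Protocol 4.1 adds that "treatment delays are permitted to allow normal count hematological recovery in the absence of PB blasts, particularly with more intensive treatment". No maximum is given for delays due to count recovery. In the guadecitabine arm, Protocol 7.3.1 lets subjects with highly proliferative disease start early: "such subsequent cycles could begin any time after treatment is completed in the preceding cycle". BSC subjects, who exist only in the treatment choice (TC) arm, follow a 28-day schedule (Table 7, footnote d). SAP 7.4.1 keeps the cycle number whatever the delay.

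**Analysis.** SAP 7.3.2.10 uses visit or treatment cycle as the time variable for the by-time summaries and for the repeated-measures model. The model terms are baseline, treatment, time and treatment by time, with an unstructured covariance. The output is "The difference of the least squares means between the two treatment groups at each time (ie, visit/treatment cycle", with a 95% CI. Data are limited to the first 6 months. SAP 5.1 explains that limit by the monthly assessment of subjects on or off treatment.

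**The concern.** A treatment contrast at a time point is interpretable when both arms are measured at about the same time since randomization. Here the label is a cycle number or visit name, and elapsed time under one label depends on how fast the subject moved through the cycles. If quality of life changes over time and cycle pace differs between arms, the contrast can be non-zero with identical courses in both arms.

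The second gap concerns subjects who stop early. Their records come from the safety visit and monthly visits, and the SAP does not say how these enter a time factor indexed by cycle. The sponsor is not blinded (Protocol 6.2), and the final database lock was still to come when SAP 6.0 was written. An open rule would therefore be settled by people able to see the data.

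At stake is a stated secondary objective, which SAP 7.3.3 intends as supportive evidence of benefit.

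**Working it through.** The documents give no EQ-5D mean, SD, slope, power or cycle-length distribution, so there is no plan figure to reproduce. The check is calendar arithmetic.

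**Step 1: days under one cycle label.** With average cycle length L, Cycle k Day 1 falls L × (k − 1) days after Cycle 1 Day 1. L = 28 is the nominal value. L = 35 and L = 42 are assumptions.

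| Label | L = 28 | L = 35 | L = 42 | 35 vs 28 | 42 vs 28 |
|---|---|---|---|---|---|
| Cycle 2 | 28 | 35 | 42 | 7 | 14 |
| Cycle 3 | 56 | 70 | 84 | 14 | 28 |
| Cycle 4 | 84 | 105 | 126 | 21 | 42 |
| Cycle 5 | 112 | 140 | 168 | 28 | 56 |
| Cycle 6 | 140 | 175 | 210 | 35 | 70 |

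With 42-day cycles, Cycle 6 Day 1 lies beyond Day 180, so the label itself drops out of the 6-month analysis. Randomization may precede Cycle 1 Day 1 by up to a week (Protocol 6.1).

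**Step 2: nominal cycles against 30-day months.** The gap is (30 − 28) × (k − 1), which is 2 days at Cycle 2 and 10 days at Cycle 6. If cycles run to plan, the mismatch is minor.

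**Step 3: off-treatment records.** Take a subject whose last dose is on Day 5 of Cycle 1. The safety visit falls at Day 5 + 30 = 35 (up to 42). Monthly visits counted from Day 35 fall near Days 65, 95, 125 and 155. With a last dose on Day 12, the safety visit is at Day 42 (up to 49), with visits near Days 72, 102, 132 and 162. None of these has a cycle number.

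**Step 4: what the time factor could mean.**
- Cycle labels only: the Step 3 records drop out. That loses the advantage SAP 5.1 gives for the 6-month limit, namely assessment whether or not treatment continues.
- Every named visit is its own level: a follow-up level pools records at different elapsed times, and the unstructured covariance needs pairs of levels that few subjects share.
- Monthly visits matched to cycle numbers: workable near 28 days (Step 2), but the SAP states no such rule.

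**Step 5: illustration under no treatment effect.** Spurious difference = change per day × offset. Suppose one arm averages 35-day cycles and the other 28, and the index changes by 0.01, 0.02 or 0.05 per 28 days in both arms (all assumptions). At Cycle 6 the difference is 35/28 times the slope: 0.0125, 0.025 or 0.0625. With equal cycle lengths it is zero.

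**The case against.** The strongest reply is that this is missing detail, not a demonstrated bias. Delays for count recovery require the absence of peripheral blasts. With active leukemia, Protocol 7.1.2 gives the second guadecitabine cycle without delay, and Table 5 keeps later cycles on schedule when blasts are present. In the Phase 2 cohort, 75 of 103 subjects were nonresponders (Protocol Table 2), so many may never qualify for a delay. Protocol 4.1 expects delays with intensive regimens in both arms, which may partly cancel. A 28-day cycle is close to monthly, and the reason in SAP 5.1 concerns continued collection rather than exact day alignment. Windows could also exist in programming specifications.

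Most of this stands as a limit on size. It rules out several stronger readings:

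- A reader might infer that the safety visit is one model time point, pooling a subject who stops after one cycle with one who stops after six, months apart. The SAP does not say the safety visit is a level of the time factor, and that comparison is between two individuals, not two arms.
- A reader might set delayed cycles against monthly off-treatment visits and read off a false difference of several EQ VAS points. That needs one arm mostly on treatment and the other mostly off, a shared label, and a slope. The documents support none of these.
- A reader might infer that on-treatment values are typically taken after count recovery. The no-delay rules above contradict this as a general statement.

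The reply does not remove the gap. The SAP names a time variable that ignores elapsed days and gives no mapping for off-treatment records. The protocol also builds in features that differ by arm: early cycles for guadecitabine, a fixed 28-day schedule for BSC, and TC duration set by local practice.

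**Conclusion.** The concern holds as a defect in the definition of analysis time. Equal labels can mean different days since randomization, possibly differently by arm, and records after discontinuation have no cycle label.

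The size and direction cannot be computed. The offset is small if cycles stay near 28 days. It reaches 35 days at Cycle 6 if one arm averages 35-day cycles against 28, which is an assumption. The documents do not show that the arms actually differ in cycle pace, so a reader should not conclude that the EQ-5D result will be biased.

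Nor does the point touch the trial's main conclusion. EQ-5D is outside the testing hierarchy (SAP 7.3.3), so overall survival and type I error control are unaffected. It is still worth correcting before database lock, because arm differences with confidence intervals are to be presented as supportive evidence.

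**What to change.** In SAP 7.3.2.10, replace visit or treatment cycle with non-overlapping windows counted from randomization. Use the 30-day month that SAP 7.3.2.3 already adopts, with targets at Days 30, 60, 90, 120, 150 and 180. An example is Days 16–45, 46–75, 76–105, 106–135, 136–165 and 166–180, the last closing at Day 180 to respect the 6-month limit.

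- Map post-baseline EQ-5D records to windows whether on or off treatment and whatever the visit name.
- Use the record closest to target, with a stated tie rule.
- Use the windows as the time factor in the mixed model and in the by-time summaries. A by-cycle summary can stay as descriptive.
- State what happens to a record before Day 16. An early second guadecitabine cycle could produce one, since dosing on Days 1–10 allows a start from Day 11.

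On-schedule subjects fit: with a randomization-to-treatment gap of 0 to 7 days, 28-day cycles give Days 28–35, 56–63, 84–91, 112–119, 140–147 and 168–175, one window each.

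The cost is SAP wording and one derived variable from assessment dates, which I take to be in the database. There are two downsides. Subjects with delayed cycles will have empty windows. Regular 42-day cycles starting at randomization give Days 42, 84, 126 and 168, leaving 46–75 and 136–165 empty, and such gaps may be informative. Values from different points in the cycle will also still share a window.

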7.3.3 Test Sequence and Procedures of Statistical Tests for Efficacy Endpoints

To control the alpha errors associated with testing the multiple endpoints, the primary endpoint, OS, will be tested first. If OS reaches statistical significance in favor of guadecitabine, a hierarchical analysis of secondary endpoints will proceed in the following pre-specified order:

- 1) EFS.
- 2) Survival rate at 1 year after randomization.
- 3) NDAOH during the first 6 months.
- 4) Transfusion independence rate.
- 5) Combined CR + CRh rate
- 6) CRc (CR+CRi+CRp) rate.
- 7) HCT rate.

A statistically significant test result in favor of guadecitabine for a given endpoint serves as a gatekeeper (Westfall and Krishen 2001) for the testing of statistical significance to proceed to a subsequent secondary endpoint. The overall alpha error rate is controlled at the 0.05 level by following the above testing sequence and procedures.

The efficacy endpoints of duration of combined CR and CRh and Health Related QOL will be used as supportive evidence of the beneficial treatment effect and will therefore, not be included in the hierarchical testing to control alpha error. Differences of treatment effect for these endpoints and associated 95% CIs, if applicable, will be constructed.

7.3.4 Subgroup Analysis

Subgroup analyses will be performed to explore how the treatment effect on OS is influenced by baseline variables, extent of treatment received, and the individual TC therapy administered. To evaluate the treatment effect at different levels of each of these variables, the Kaplan-Meier analysis and Cox model will be performed separately by each level of each variable as follows:

- Age ($<65, \geq 65$).
- Age ($<75, \geq 75$).
- Sex (Male, Female).
- Baseline cytogenetic risk (poor-risk, others).
- Baseline ECOG performance status (0-1, 2).
- Response to initial intensive induction therapy (refractory, first relapse, >1 relapse).
- Prior HCT (yes, no).
- Baseline BM blasts ($\leq 40\%$, >40%).

- Baseline PB blasts ($\leq 30\%$, >30%).
- Baseline total WBC counts ($\leq 20,000/\mu$ L, $> 20,000/\mu$ L).
- Study center region (North America, ROW).
- Race (White, Black, Asian, Other).
- Presence of baseline genetic mutations or gene expressions for each gene such as FLT3-ITD, NPM1, CEBPA biallelic, TP53, ASXL-1, and RUNX-1 (yes, no).
- Treatment cycles received (<4 cycles vs \geq 4 cycles).
- Treatment cycles received (<6 cycles vs \geq 6 cycles).
- Individual preselected TC (high intensity, low intensity, BSC).

The treatment effect (HR and 95% CI) for each of these subgroups will be displayed on Forest plots.

Subjects with missing a value for a variable used to define a subgroup will be excluded from that subgroup analysis except for subgroups with an "Other" category. In those subgroups, subjects with missing values will be included in the Other category.

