5.4.1 Discontinuation from Study Treatment

Subjects who discontinue study treatment will still continue study follow-up procedures. Investigators are encouraged to assess all subjects according to the study protocol even after discontinuation from study treatment.

- Investigators can discontinue subjects from study treatment in case of unacceptable toxicity, non-compliance, disease progression requiring alternative therapy, or if the investigator determines it is in the subject's best interest.
- Astex Pharmaceuticals may require that a subject is discontinued from treatment for safety reasons or for noncompliance.

In all cases, the reason(s) for discontinuation from study treatment must be recorded in the source document and on the relevant page of the subject's case report form or electronic case report form (CRF/eCRF).

It is important to obtain protocol-specified follow-up information on any subject discontinued from study treatment. Section 10.0 describes follow-up for AEs. Subjects should be followed for survival information until death, withdrawal of consent, or termination of the clinical trial. Safety should be followed for 30 days after the last dose of study treatment, or until the subject starts alternative anti-leukemia treatment for AML (except for hydroxyurea as specified in Section 7.4.1), whichever happens earlier (see Section 10.4). Collection of AEs and concomitant medications may also continue until the decision is made to permanently discontinue study treatment. Subjects in the BSC group will be considered to be on study treatment until they have disease progression.

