6.1 Randomization

Eligible subjects will be randomly assigned to study treatment. Treatment assignments for the individual subjects will be determined through a computer generated randomization scheme and accessed through an interactive response system. Instructions for access and use of the interactive response system for randomization will be provided to participating study centers separately.

Randomization will be 1:1 between guadecitabine and TC groups, and will be stratified by intensity of preselected TC option (high intensity vs low intensity vs BSC), ECOG performance status (0-1 vs 2), baseline cytogenetics (poor risk vs other; see Appendix 3), and study center region (North America vs ROW).

Selection of 1 of the TCs must be made prior to the randomization of each subject. Subjects should receive study treatment as soon as possible after randomization (maximum of 1 week between randomization and treatment).

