11.6.3 Subgroup and Exploratory Analyses

Subgroup analyses will be performed to explore how OS is influenced by baseline variables and the individual TC therapy administered, and to evaluate the treatment effect at different levels of each of these variables. The Kaplan-Meier analysis and Cox model will be performed by subgroup levels of the baseline variables and each TC therapy listed below:

- Age ($<75, \geq 75$).
- Baseline cytogenetic risk (poor-risk, others; see Appendix 3).
- ECOG performance status (0-1, 2).
- Number of prior regimens ($\leq 2, >2$).
- Prior HCT (yes, no).
- Baseline BM blasts ($\leq 40\%$, >40%).

- Baseline total WBC counts ($\leq 20,000/\mu$ L, $> 20,000/\mu$ L).
- Study center region (North America, Europe, Asia-Pacific, Other).
- Race (White, Black, Asian, Other).
- Presence of baseline specific gene mutations or gene expressions for each gene (yes, no).
- Individual preselected TC (high intensity, low intensity, BSC).
- Additional subgroups may also be further described in the Statistical Analysis Plan.

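### SAP 7.3.4 compares OS between arms within levels of cycles received, a post-randomization variable that accrues differently by arm, so these hazard ratios can show an effect where none exists

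*SAP*

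**What the plan says.** SAP 7.3.4 opens: "Subgroup analyses will be performed to explore how the treatment effect on OS is influenced by baseline variables, extent of treatment received", and then adds the individual TC therapy. One entry in its list begins "Treatment cycles received (<4 cycles vs" and sets that level against 4 or more; a parallel entry cuts at 6. A Kaplan-Meier analysis and a Cox model are run separately in each level of each listed variable. The hazard ratio and its 95% CI "for each of these subgroups will be displayed on Forest plots". No landmark, time-dependent method or interpretive caution is attached to the two cycle entries.

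Protocol 11.6.3 has no cycles-received subgroup, but it allows for one: "Additional subgroups may also be further described in the Statistical Analysis Plan". This is a choice of analysis, not a deviation from the protocol.

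The rules that decide how many cycles a subject receives differ by arm:

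- **Guadecitabine:** intended for at least 6 cycles unless toxicity or progression intervenes (Protocol 7.1.2; SAP 3.1). Cycles may start early in proliferative disease (Protocol 7.3.1).
- **TC:** duration follows local labelling and practice (SAP 3.1) and may include consolidation cycles (Protocol 7.2).
- **BSC:** Day 1 visits stand in for cycles (SAP 7.4.1), and Protocol 5.4.1 says "Subjects in the BSC group will be considered to be on study treatment until they have disease progression".

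**The concern.** OS runs from randomization (SAP 7.3.1), but cycles received is known only later. A subject must survive to the start of cycle 4 or 6 to enter the upper level, so level membership is partly an outcome. Because the arms accrue cycles under different rules, a given level selects different kinds of subject in each arm, and randomization no longer protects the comparison.

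The documents point to bias in both directions. Protocol 5.4.1 lists the grounds for stopping: "Investigators can discontinue subjects from study treatment in case of unacceptable toxicity, non-compliance, disease progression requiring alternative therapy", among others. Subjects with a poor prognosis may therefore stop sooner. SAP 3.1 says younger, healthier subjects tend to be given higher-intensity TC and to live longer, so fitter TC subjects may finish short courses (an assumption).

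What is at stake is how the plots are read. Enrollment stopped for futility, and Protocol 7.1.2 says a full response to guadecitabine can take six cycles or longer. A hazard ratio below 1 in the ≥6-cycle row would invite the reading that the drug works in subjects who receive enough of it.

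**Working it through.** **Inputs.** Median OS of 4.5 months (TC) and 6.5 months (guadecitabine) come from Protocol 11.1 and SAP 4.0. The 28-day cycle is in Protocol 4.1, and about 300 subjects randomized in Protocol 5.1. Treatment starts after a "maximum of 1 week between randomization and treatment" (Protocol 6.1). Protocol 4.1 adds that "treatment delays are permitted to allow normal count hematological recovery in the absence of PB blasts". The documents give no stopping rates, TC mix or link between stopping and prognosis.

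**The plan's own figure.** The plan states no figure for these subgroups. Its sample size does reproduce: at HR 4.5/6.5 = 0.692, two-sided alpha 0.05 and 90% power, Schoenfeld's formula gives 311 events and Freedman's 318, against 315 stated.

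**Step 1: survival needed to enter the upper level.** Cycle 4 starts 3 × 28 = 84 days after first treatment, so 84–91 days after randomization. Cycle 6 starts 5 × 28 = 140 days after first treatment, so 140–147 days. Permitted delays push both later. With exponential OS, the proportion dead before day d is 1 − 2^(−d/(median × 30.44)):

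| Median OS | Day 84 | Day 91 | Day 140 | Day 147 |
|---|---|---|---|---|
| 4.5 months | 35% | 37% | 51% | 52% |
| 6.5 months | 25% | 27% | 39% | 40% |

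**Step 2: the mechanism by hand.** Take identical OS in both arms (median 4.5 months) and stopping unrelated to prognosis, 15% per cycle on guadecitabine and 30% on TC (assumed).

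- Alive at day 84: 0.654 in each arm.
- Not stopped before cycle 4: 0.85³ = 0.614 on guadecitabine; 0.70³ = 0.343 on TC.
- Share in the <4 level: 1 − 0.654 × 0.614 = 0.598; 1 − 0.654 × 0.343 = 0.776.
- Early deaths as a share of that level: 0.346/0.598 = 58%; 0.346/0.776 = 45%.

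The guadecitabine side of the <4 row is richer in early deaths although survival is the same in both arms.

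**Step 3: simulation with no treatment effect.** 300 subjects 1:1; identical OS with log-normal frailty (SD 1) calibrated to either median (plain exponential OS was also run where stopping is unrelated to prognosis); censoring uniform over 365–900 days. Cycles received is the smaller of a geometric stopping count and floor(follow-up days/28) + 1. Per-cycle stopping is 15% guadecitabine and 20% TC unless stated. A prognosis link shifts the stopping logit by 0.5 or 1.0 per SD of prognosis. Entries are mean unstratified Cox hazard ratios, guadecitabine versus TC; ranges span medians and link strengths.

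| Stopping pattern (assumed) | <4 cycles | ≥4 cycles |
|---|---|---|
| Same rule in both arms (15%/15%) | 0.99–1.02 | 0.99–1.02 |
| Faster on TC, unrelated to prognosis | 1.09–1.10 (1.21–1.25 at 15%/30%) | 0.99–1.00 |
| Poor prognosis stops sooner, both arms | 1.11 | 1.04–1.08 |
| Good prognosis stops sooner, both arms | 1.04–1.08 | 0.92–0.95 |
| Poor prognosis stops sooner, guadecitabine only | 1.23–1.35 | 0.81–0.91 |
| Poor prognosis stops sooner, TC only | 0.91–1.00 | 1.16–1.30 |
| Fitter subjects stop sooner, TC only | 1.23–1.33 | 0.69–0.83 |

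Over the 15%/20% patterns the <6 row spans 0.90–1.32 and the ≥6 row 0.58–1.43. The all-subjects hazard ratio is 0.99–1.01 across all runs.

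**Step 4: checks.**

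- A 0–7 day start lag plus a mean 5-day cycle lengthening moves the 15%/20% <4 and ≥4 values by at most 0.03.
- Early cycles alone (21-day cycles in the worst-prognosis 20–40% of guadecitabine subjects, 15%/15% stopping) give ≥4 of 1.02–1.06 and ≥6 of 1.03–1.09.
- A separate simulation with other patterns agrees. One rule for both arms gives 0.99–1.01. Capping 30% or 50% of TC subjects at two cycles gives <4 of 1.10–1.26 or 1.15–1.39. At a median of 4.5 months and a shared-frailty variance of 0.5, the 95% CI for that row excludes 1 in 36% or 65% of null trials, against about 5% for the all-subjects estimate.

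**The case against.** The strongest reply concerns importance. SAP 7.3.4 says these analyses explore, names extent of treatment separately from baseline variables, and sits outside the testing hierarchy of SAP 7.3.3. Protocol 11.6.3 allows added subgroups. Two of about 16 subgroup variables are affected, in a trial already closed for futility. All of that stands, and it limits the severity.

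The size is also assumption-driven. Under one common stopping rule nothing goes wrong, so death truncation alone creates no spurious effect; the difference between arms does the work. The largest hazard ratios need prognosis to drive stopping in only one arm, while the stopping grounds in Protocol 5.4.1 apply to subjects generally. With the link in both arms the shifts are modest: when poor prognosis stops sooner, the 95% CIs exclude 1 in about 5–12% of null trials. The ≥6 level is also small, about 40–90 of 300 subjects, so its CI will be wide. These points stand too, and the one-arm rows above should be read as extremes.

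They do not rescue the analysis. The documents themselves set different duration rules by arm, so the benign case of one common rule is not the one planned. Even without a prognosis link, 15%/30% stopping gives <4 of 1.21–1.25, and in a 600-trial repeat the CI excluded 1 in 27–32% of null trials. Naming extent of treatment separately does not help when the model, the plot and the treatment-effect label are the same as for baseline factors.

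**Conclusion.** The concern holds. The between-arm hazard ratios by cycles received are not randomized comparisons and can depart from 1 in either direction with no true effect. That rests on three features of the plan: OS starts at randomization, cycles are counted afterwards and end at death, and the arms follow different duration rules.

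The size rests on assumed stopping patterns and cannot be predicted from the documents. Plausible values run from about no distortion to roughly 0.7–1.35 at the 4-cycle cut and 0.6–1.4 at the 6-cycle cut. The primary OS test, its conclusion and the hierarchy are unaffected. The change should be made because the rows can mislead and removing them costs almost nothing.

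**What to change.** Delete the two cycles-received entries from SAP 7.3.4 and its Forest plots, together with the words on extent of treatment in its opening sentence. Report cycles received descriptively by arm under SAP 7.4.1, which already tabulates them.

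If the question is kept, move it to a separate time-dependent or landmark analysis labelled descriptive and non-randomized. State the time origin and how early cycles are counted. Set any landmark later than day 91 (cycle 4) or day 147 (cycle 6) after randomization, with a stated allowance for permitted delays. A landmark removes the death truncation but still conditions on a post-randomization variable. It would also exclude the 27–37% (day 91) or 40–52% (day 147) expected to have died by then at the plan's medians.

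The cost is SAP wording and two exploratory rows; the optional analysis is minor programming. The 315-event calculation and the primary analysis do not change.
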